The initial protocol submitted and approved by the Duke IRB was intended to focus solely on the design and procedures for Aim 1 in order to address the three aims listed below in sequential order such that the findings from Aim 1 would be used to further develop the protocol design and procedures for Aim 2, and similarly the findings from Aims 1 and 2 will strengthen the approach to Aim 3.

This study will enroll up to 40-60 total participants for Aim-2 and Aim-3. While we anticipate that the screening blood draw will yield a number of screen failures, we expect that approximately 20-25 subjects will complete Aim-2 and 15-20 will complete Aim-3 of the study protocol.

Enrolled participants for Aim-2 will be asked to complete three study visits including the consent visit and two infusion study visits that will include hyperglycemic clamps and an infusion of Exedin-9. Each

infusion procedure will last 2 hours.

AIM-2: The primary outcome for visits 2-3 will be to measure the effects of Ex-9 on fasting glucose-stimulated insulin secretion before and after experimentally induced insulin resistance. The primary experimental variable for analysis will be C-peptide during the clamp. Mean values will be compared between the period of glucose only stimulation and glucose with Ex-9. For each subject in the active treatment arm data will be analyzed using 2-way ANOVA for repeated measures using time (0-60 vs 60-120 min) and treatment (Dex vs no Dex) as the two factors. Based on our previous studies we expect a significant time effect due to Ex-9. If there is an interaction with treatment we would conclude that experimental insulin resistance influences the fasting GLP-1 effect. Data from control subjects will be analyzed identically; here we expect no interaction, indicating that the fasting GLP-1 is a stable measure. In our previous study using Ex-9 during a glucose clamp, the average coefficient of variation in insulin concentrations at the conclusion of each step in the ramp was 30%. Using this estimate of between subject variation, detecting a 20% difference between subsequent steps in the GLP-1 ramp with a power of 80% and significance level of 0.05 will require 8 subjects.

Enrolled participants for Aim-3 will be asked to complete two study visits including the consent visit and one infusion study visit that will include a hyperglycemic clamp and an infusion of Exedin-9. The infusion procedure will last 2 hours.

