Subjects will have two intravenous catheters placed, one in each arm: 1) for blood drawing, and 2) for the infusion of test materials. The arm for blood draws will be heated to maintain blood flow and arterialize venous blood. Four (4.0 ml) fasting blood samples will be taken at -15, -10, -5 and 0 minutes and then a variable infusion of 20% dextrose will begin to clamp the blood glucose at basal +3 mM for 120 minutes. This hyperglycemic clamp will be stabilized over 60 minutes and 4.0 ml blood samples will be taken every 5-10 minutes during this period to establish baseline insulin secretion and active GLP-1 levels. During these visits, participants will receive an infusion of Exendin-9 (750 pmol/kg/min) between the 60 and 120 minute time-points of the clamp procedure. For consistency, blood draws (4.0 ml) will occur every 5-10 minutes between the 60 and 120 minute time-points of both visit 2 and 3. Upon completion of the final 60-minute interval for the Ex-9 infusion, both the infusion and clamp procedures will be complete. One additional blood sample (1 ml) will be drawn post the assessment to be tested immediately with the YSI glucose analyzer to ensure glucose levels are within normal limits. **Visit 3** will occur at least one week later and will be a repeat infusion procedure identical to **Visit 2**. The total amount of blood collected during each of these visits will be a maximum of ~141 ml (~9.5 Tbsp).

We will aim to complete studies in 10-15 subjects before and after approximately one week of dexamethasone(Dex) treatment to induce insulin resistance. Insulin resistance in response to a short-course (4 mg daily) of supraphysiologic glucocorticoids is an established research procedure and is completely reversible over the course of exposure we are proposing. However, the rate of reversal is variable among subjects preventing a straight counter-balanced allocation to treatment (i.e. half of subjects getting Dex before the first study and half before the second). Therefore we will enroll 6-10 subjects as controls for effects of time and repeat testing. These individuals will have identical clamps with no dexamethasone at approximately 1 week intervals and will be determined at random by study staff.

AIM-3

Approximately 15-20 subjects will complete AIM-3 of the study and these participants will have two study visits – a baseline consent visit, and one infusion procedures.

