to target accrual and accrual rate. Describe interim analysis including plans to stop accrual during
monitoring. Phase I studies, include dose escalation schema and criteria for dose escalation with
definition of MTD and DLT.

AIM-2 – The primary outcome for visits 2-3 will be to measure the effects of Ex-9 on fasting glucose-stimulated insulin secretion before and after experimentally induced insulin resistance. The primary experimental variable for analysis will be C-peptide during the clamp. Mean values will be compared between the period of glucose only stimulation and glucose with Ex-9. For each subject in the active treatment arm data will be analyzed using 2-way ANOVA for repeated measures using time (0-60 vs 60-120 min) and treatment (Dex vs no Dex) as the two factors. Based on our previous studies we expect a significant time effect due to Ex-9. If there is an interaction with treatment we would conclude that experimental insulin resistance influences the *fasting GLP-1 effect*. Data from control subjects will be analyzed identically; here we expect no interaction, indicating that the fasting GLP-1 is a stable measure. In our previous study using Ex-9 during a glucose clamp, the average coefficient of variation in insulin concentrations at the conclusion of each step in the ramp was 30%. Using this estimate of between subject variation, detecting a 20% difference between subsequent steps in the GLP-1 ramp with a power of 80% and significance level of 0.05 will require 8 subjects.

AIM-3 – The primary outcome measure for this study will be the fasting GLP-1 effect. This will be defined as the difference in steady state glucose-stimulated insulin secretion with and without Ex-9. The difference will be expressed as a percentage of glucose stimulated insulin secretion without Ex-9, and serve as the primary variable for comparison among the lean, obese and diabetes cohorts.

Data & Safety Monitoring

Summarize safety concerns, and describe the methods to monitor research subjects and their data to
ensure their safety, including who will monitor the data, and the frequency of such monitoring. If a
data monitoring committee will be used, describe its operation, including stopping rules and frequency
of review, and if it is independent of the sponsor (per 45 CFR 46.111(a) (6)).

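### Aim 2 draws its dexamethasone conclusion from an arm in which dexamethasone always comes second, and never formally compares that arm with the no-dexamethasone controls

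*Combined protocol and SAP*

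**What the plan says.** Design & Procedures, AIM-2, fixes the order of testing: "We will aim to complete studies in 10-15 subjects before and after approximately one week of dexamethasone(Dex) treatment to induce insulin resistance". It explains why the order is not balanced: "However, the rate of reversal is variable among subjects preventing a straight counter-balanced allocation to treatment". It then adds a comparison group for that reason: "Therefore we will enroll 6-10 subjects as controls for effects of time and repeat testing". On how that group is formed it says: "These individuals will have identical clamps with no dexamethasone at approximately 1 week intervals and will be determined at random by study staff".

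Data Analysis & Statistical Considerations, AIM-2, names C-peptide during the clamp as the primary variable and specifies the model for one arm only: "For each subject in the active treatment arm data will be analyzed using 2-way ANOVA for repeated measures using time", meaning the 0-60 against the 60-120 min period, with Dex versus no Dex as the second factor. The decision rule, given there and in the Research Abstract, is: "If there is an interaction with treatment we would conclude that experimental insulin resistance influences the fasting GLP-1 effect". The controls are handled in one sentence: "Data from control subjects will be analyzed identically; here we expect no interaction, indicating that the fasting GLP-1 is a stable measure".

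No section contains an arm factor, a between-arm contrast, or a statement of what follows if the controls do show an interaction.

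**The concern.** In the Dex arm every subject has the no-Dex clamp first and the Dex clamp second. The treatment factor and the visit factor are therefore one factor, and the period-by-treatment interaction cannot separate a Dex effect from a change in the Ex-9 response that comes with repeat testing. The protocol recognises this and enrols randomly determined controls to deal with it, but the analysis does not use them for that purpose.

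The controls have no Dex level, so an identical analysis can only mean period by visit, which is the term confounded with Dex in the active arm. Testing it is a formal test, but its role is informal: nothing ties its result to the Dex conclusion. Two faults follow. Finding significance in one arm and not in the other is not a test of the difference between them. And a non-significant result in 6-10 people is read as evidence of stability.

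At stake is the primary Aim 2 conclusion, that insulin resistance alters the fasting GLP-1 effect. A repeat-test shift could be credited to Dex or, in the opposite direction, could hide a real Dex effect.

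**Working it through.** **The plan's own figure.** The plan states 8 subjects for a 20% difference with 30% CV, 80% power and alpha 0.05. Taking 30% as the SD of a paired difference, n = (0.30 × (1.960 + 0.842) / 0.20)² = 17.7, so 18 (20 with the t distribution); two independent groups need 36 each. Eight is reached two-sided only with an unstated within-subject correlation of about 0.77-0.80 (normal) or 0.83-0.86 (t). This is a separate weakness. The figure concerns insulin at steps of a GLP-1 ramp and supplies no SD for the C-peptide interaction.

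**The contrast.** For each subject let d = [mean C-peptide 60-120 minus 0-60 min at Visit 3] minus [the same at Visit 2]. The two-by-two within-subject interaction test is a one-sample t test on d. With Dex effect δ and repeat-test shift π in the Ex-9 response:

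- Dex arm: E(d) = δ + π
- Controls: E(d) = π
- Dex minus control: E = δ

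A visit change common to both periods cancels within d. Only a change that differs between the two periods contributes to π.

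**Inputs.** Arm sizes 10-15 and 6-10 are from Design & Procedures. Assumed, because the documents do not give them: SD of d = 1 in both arms, the same π in both arms, normal d, two-sided 0.05, and δ = 0.

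**Formula.** Each one-sample rejection rate comes from the noncentral t with n − 1 df and noncentrality π√n. For π = 0.5 the noncentrality is 1.58 (n=10), 1.94 (n=15) and 1.22 (n=6), giving 0.293, 0.438 and 0.171.

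The plan does not say how the control result enters the conclusion, so two readings are shown. Reading A uses the Dex arm alone. Reading B requires Dex significant and controls non-significant, with probability P(Dex) × (1 − P(control)); for 10 vs 6 at 0.5 SD, 0.293 × (1 − 0.171) = 0.243.

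| Shift (SD) | A: n=10 | A: n=15 | Control detects: n=6 | n=10 | B: 10 vs 6 | 15 vs 6 | 10 vs 10 | 15 vs 10 |
|---|---|---|---|---|---|---|---|---|
| 0 | 0.050 | 0.050 | 0.050 | 0.050 | 0.048 | 0.048 | 0.048 | 0.048 |
| 0.1 | 0.059 | 0.065 | 0.055 | 0.059 | 0.056 | 0.062 | 0.056 | 0.061 |
| 0.25 | 0.109 | 0.147 | 0.080 | 0.109 | 0.101 | 0.136 | 0.097 | 0.131 |
| 0.5 | 0.293 | 0.438 | 0.171 | 0.293 | 0.243 | 0.363 | 0.207 | 0.310 |
| 0.75 | 0.562 | 0.771 | 0.321 | 0.562 | 0.382 | 0.524 | 0.246 | 0.338 |
| 1 | 0.803 | 0.949 | 0.507 | 0.803 | 0.396 | 0.468 | 0.158 | 0.187 |

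The false rate reaches 10% at a shift of 0.18-0.23 SD under A and 0.19-0.26 SD under B.

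**What the controls can show.** The 95% CI half-width for their mean change is t/√n: 2.571/√6 = 1.05 SD and 2.262/√10 = 0.72 SD.

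**Between-arm test.** Simulation, 200,000 runs per cell, shifts 0 and 0.5 SD, no Dex effect:

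| Dex-arm SD / control SD | Welch rejects | Pooled t rejects |
|---|---|---|
| 1 | 4.8-5.3% | 4.9-5.1% |
| 1.5 | 4.8-5.0% | 2.3-5.2% |
| 0.67 | 5.0-5.4% | 5.2-9.8% |

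**Masking.** A true 1 SD Dex effect with a −0.5 SD shift leaves a net 0.5 SD in the Dex arm. Its power falls from 0.803-0.949 to 0.293-0.438. The between-arm contrast is unaffected because π cancels.

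**The case against.** The protocol has not overlooked the problem. It names the order effect, says why counter-balancing is not used, recruits concurrent controls at random, and tests the right term in them. What is missing is a between-arm test and a rule for a positive control result. That is accepted, but these are what turn the controls from reassurance into a correction.

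The harm is conditional. No document shows a repeat-test shift in the Ex-9 response, the plan expects none, a shift common to both periods cancels, and at 0.1 SD the false rate is only 6-7%. All of this stands. But the investigators thought the risk worth 6-10 extra subjects, and the first period includes the clamp's stabilisation, so a visit difference confined to one period cannot be ruled out from the documents.

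The control check is not useless. With 10 controls and a 1 SD shift it cuts the false rate from 80-95% to 16-19%. This stands for large shifts and the larger control group. With 6 controls, or shifts near 0.5 SD, the check does little.

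Scale is a fair point too. If Dex raised C-peptide overall and Ex-9 removed the same percentage, the raw difference would still change and the between-arm test could reject. That comes from the plan's own additive C-peptide model, not from the comparison of arms, and it applies equally to the planned test. Aim 3 uses a percentage, so the choice of scale for Aim 2 deserves its own justification.

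Finally, Welch on raw change is not the only remedy. A baseline-adjusted ANCOVA or an arm-by-visit-by-period term would also close the gap. The essential step is the between-arm comparison.

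**Conclusion.** The concern holds. As written, the Aim 2 conclusion rests on a contrast equal to the Dex effect plus any repeat-test shift, and the randomly determined controls enrolled against that shift are left out of the inference. This follows from the design and the analysis text, without any assumed number.

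The size does depend on assumptions. At a shared 0.5 SD shift, false Dex conclusions arise in 29-44% of trials (Dex arm alone) or 21-36% (with the control check), while 6-10 controls detect that shift only 17-29% of the time. At zero shift the planned rule is correctly sized. Because the defect lies in the primary Aim 2 inference and the data to correct it are already planned, the change should be required.

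**What to change.** Base the Aim 2 Dex conclusion on the Dex-minus-control difference, with its 95% CI, in each subject's Visit 2 to Visit 3 change in (60-120 minus 0-60 min mean C-peptide). Test it with an unequal-variance (Welch) two-sample t test, since Dex may alter the spread of C-peptide. Keep the within-arm interactions as supportive. Replace the inference of stability from a missing control interaction with the control-arm mean change and its 95% CI.

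No new data or enrolment is needed, but precision is lost and the plan should say so. Ranges cover 10 vs 6 to 15 vs 10 subjects:

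- **Standard error**, equal SDs: √(1/a + 1/b) / √(1/a) = 1.63 (10 vs 6), 1.87 (15 vs 6), 1.41 (10 vs 10) and 1.58 (15 vs 10) times that of the Dex-arm-only test.
- **Power for a true 1 SD effect**, equal SDs: 42-64%, against 80-95% for the Dex arm alone.
- **Power for an effect of 1 control SD, unequal SDs:** 31-48% (Dex arm alone 47-67%) if the Dex-arm SD is 1.5 times control; 48-74% (99-100%) if it is 0.67 times.
- **Effect detectable with 80% power**, equal SDs: 1.21-1.62 SD, against 0.78-1.00 SD.
- **Mean 95% CI half-width**, equal SDs: 0.85-1.13 SD.

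The extra power of the within-arm test comes from assuming the zero shift that the controls were enrolled to check. The plan should also state that a non-significant between-arm result is not evidence of no Dex effect.

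### Absence of an interaction in 6-10 controls cannot by itself show that the fasting GLP-1 effect is stable, and the plan sets no interval or margin that could

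*Combined protocol and SAP*

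**What the plan says.** The Aim 2 analysis is given in Data Analysis & Statistical Considerations and repeated in the Research Abstract. On the outcome it says "The primary experimental variable for analysis will be C-peptide during the clamp". The dexamethasone arm is to be analysed by "2-way ANOVA for repeated measures using time (0-60 vs 60-120 min) and treatment (Dex vs no Dex) as the two factors", and an interaction there is to be read as an influence of insulin resistance on the fasting GLP-1 effect.

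For the other arm, "Data from control subjects will be analyzed identically", and "here we expect no interaction, indicating that the fasting GLP-1 is a stable measure".

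The group sizes are in Design & Procedures, AIM-2. For the active arm: "We will aim to complete studies in 10-15 subjects before and after approximately one week of dexamethasone(Dex) treatment". For the comparison arm: "Therefore we will enroll 6-10 subjects as controls for effects of time and repeat testing", and "These individuals will have identical clamps with no dexamethasone at approximately 1 week intervals". The same paragraph explains that a counter-balanced order was ruled out because recovery from dexamethasone varies between subjects.

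The only sample-size statement arrives at 8 subjects. It concerns a 20% difference between successive steps of a GLP-1 ramp and uses an insulin figure: "the average coefficient of variation in insulin concentrations at the conclusion of each step in the ramp was 30" (per cent). No power, margin, interval or repeatability measure is given for the control interaction.

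**The concern.** The control sentence gives the inference to be drawn from a null: no interaction is taken to indicate stability. A non-significant interaction can mean that the Ex-9 effect did not change between clamps, or that the data were too few to show that it did. Only an interval set against a margin separates the two, and the plan has neither.

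This matters because every dexamethasone subject has the treated clamp second, so treatment and visit order are confounded in the active arm. The controls are the plan's stated protection against reading drift, or a repeat-clamp effect, as a dexamethasone effect. If an inconclusive null in 6-10 people is written up as stability, that protection looks stronger than it is.

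**Working it through.** **1. The plan's own figure.** Inputs as stated: difference 20%, CV 30%, power 80%, alpha 0.05 (taken as two-sided; the text does not say).
- Paired comparison with an SD of the difference of 30%: n = (0.30 × (1.960 + 0.842) / 0.20)² = 17.7, so 18 by the normal formula, or 20 with the t distribution.
- Two independent groups: 2 × 17.7 = 35.3, so 36 per group.
- The stated 8 appears only if the SD of the paired difference is about 17.3% (t) or 20.2% (normal). From SD of difference = 0.30 × √(2(1 − ρ)), that needs a within-subject correlation of about 0.83 or 0.77, which the plan does not state.

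This figure is for one step-to-step insulin difference. It is not a calculation for the control interaction, and is used below only as a source of assumed SDs.

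**2. The test.** With two periods and two visits, the repeated-measures interaction equals a one-sample t-test on each subject's difference of differences: the Ex-9 change at the second clamp minus the Ex-9 change at the first. Let δ be the true shift divided by the SD of this contrast. The chance of a non-significant result is P(|T| ≤ t(0.975, n−1)), where T is noncentral t with n−1 degrees of freedom and noncentrality δ√n.

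| | n = 6 | n = 8 | n = 10 |
|---|---|---|---|
| Missed, shift 0.5 SD | 83% | 77% | 71% |
| Missed, shift 1.0 SD | 49% | 32% | 20% |
| Shift missed half the time | 0.99 SD | 0.80 SD | 0.69 SD |
| Shift for 80% power | 1.43 SD | 1.16 SD | 1.00 SD |
| 95% CI half-width, t(0.975, n−1)/√n | 1.05 SD | 0.84 SD | 0.72 SD |

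The third row marks where a null stops being the likelier result.

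**3. In percentage terms.** The documents give no SD for the C-peptide contrast, so three values are assumed, as a percentage of the glucose-only value:
- 17.3%: the most favourable. It treats the SD of a single paired difference as if it were the SD of the difference of differences.
- 24.5%: 17.3% × √2, for two independent differences.
- 30%: the plan's CV used directly.

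The 10- and 20-point shifts are also assumptions. Entries are for n = 6 / 8 / 10.

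| Contrast SD | 10-point shift missed | 20-point shift missed | 95% CI half-width |
|---|---|---|---|
| 17.3% | 79 / 71 / 63% | 38 / 20 / 10% | 18 / 14 / 12% |
| 24.5% | 87 / 83 / 79% | 63 / 49 / 37% | 26 / 20 / 18% |
| 30% | 90 / 87 / 84% | 73 / 63 / 53% | 31 / 25 / 21% |

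**4. What an equivalence criterion could achieve.** Take, for illustration only, a margin of ±20%, no true drift, and a requirement that the 90% CI lie inside the margin (two one-sided 5% tests). The chance of passing at n = 6 / 8 / 10 is 58 / 80 / 91% at SD 17.3%, 21 / 37 / 54% at 24.5%, and 9 / 17 / 28% at 30%.

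**The case against.** The best reply is that the control sentence is a prediction. For the dexamethasone arm the plan says what it would conclude; for controls it says only what it expects. That is fair as to tone, and nothing in the documents says that stability will be reported as a finding in its own right. But the sentence does state what the expected null would indicate, and the interaction test is the only criterion offered.

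Some stronger readings are tempting and are not supported:
- *A null is the likely result whatever the drift.* No. At a 1.0 SD shift the test detects the drift slightly more often than not at n = 6 and 80% of the time at n = 10. At SD 17.3% a 20-point shift is usually detected at all three sizes.
- *Six controls fall short of the plan's own requirement of 8.* That figure belongs to insulin at ramp steps, a different contrast in a different variable. No sample-size statement covers the control test.
- *The plan treats 20% as its smallest difference of interest.* It names no such quantity for visit-to-visit change. A 20% margin could equal or exceed the whole Ex-9 effect, whose size is not given.
- *The control analysis cannot be run.* Controls have no dexamethasone level, but the design makes it plain that their second factor is first versus second clamp. This needs only a clarifying word.

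A direct dexamethasone-versus-control comparison would address time effects on the dexamethasone conclusion more squarely. It would not show that the measure is reproducible, so it does not replace the change proposed here.

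**Conclusion.** The point holds in a limited form. Without an interval or margin, a null interaction cannot establish stability, whatever the SD. How often it would mislead depends on the size of the drift: a null is the likelier outcome only for shifts up to about 1.0 SD of the contrast with 6 controls, or about 0.7 SD with 10.

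The SD-unit results rest on a two-sided 5% test and normally distributed contrasts. The percentage results rest also on the assumed SDs, which are borrowed from an insulin figure and are not known for C-peptide. Nothing here shows that the fasting GLP-1 effect does drift; the plan as written could not tell a stable measure from an imprecisely measured one. The wording should be changed, because it affects what the control arm can be said to have shown.

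**What to change.** Replace the control sentence, in both places where it appears, with:

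*Control data will be analysed with period and visit (first versus second clamp) as factors. The visit-to-visit change in the Ex-9 effect will be reported with its 95% CI and within-subject SD. A non-significant interaction will not by itself be taken as evidence of stability. Stability will be claimed only if the CI (90%, corresponding to two one-sided 5% tests) excludes changes larger than a margin set in advance by the investigators, on the C-peptide scale and small relative to the expected Ex-9 effect. Otherwise stability will be reported as not established.*

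The investigators should choose and justify the margin; ±20% should not be written in by default. The cost is wording only, with no extra subjects or samples. The downside is that 6-10 controls may well yield a result of not established: in the ±20% illustration the chance of passing is 9-28% at SD 30% and 21-54% at 24.5%. A tighter margin, or a 95% interval as the criterion, would be harder still to meet.

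### Aim 2 reads a non-significant interaction in 6-10 controls as proof that the fasting GLP-1 effect is stable, which follows neither for mean drift nor for repeatability within a person

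*Combined protocol and SAP*

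**What the plan says.** Under Data Analysis & Statistical Considerations, AIM-2 (repeated in the Research Abstract), the outcome is set by "The primary experimental variable for analysis will be C-peptide during the clamp", and "Mean values will be compared between the period of glucose only stimulation and glucose with Ex-9". The dexamethasone arm is analysed by two-way repeated-measures ANOVA "using time (0-60 vs 60-120 min) and treatment (Dex vs no Dex) as the two factors". The control arm is to be analysed identically, and of that analysis the plan says: "here we expect no interaction, indicating that the fasting GLP-1 is a stable measure".

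Design & Procedures, AIM-2 explains why the controls exist. Reversal of the dexamethasone effect varies too much between subjects for counterbalancing, so "we will enroll 6-10 subjects as controls for effects of time and repeat testing". On the schedule: "These individuals will have identical clamps with no dexamethasone at approximately 1 week intervals".

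The documents give no within-subject SD or CV, intraclass correlation, limits of agreement, equivalence margin or other criterion for stability. The only variability figure is a 30% CV for insulin, described as between-subject. Aim 3 takes the fasting GLP-1 effect, as a percentage and from one clamp per subject, as its primary variable.

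**The concern.** The plan draws a positive conclusion about a measurement from the expected absence of a significant result. *Stable* could mean two things. One is that the group mean does not drift with time and repeat testing, which is the job Design & Procedures gives the controls. The other is that the same person gives nearly the same value twice, which is how a sentence about a measure is naturally read. The planned test cannot establish the first with 6-10 subjects and does not examine the second.

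The controls are the evidence that a change seen after dexamethasone is not simply an effect of testing twice. If absence of drift is declared from non-significance, that evidence is weaker than it appears. Aim 3 then measures the same parameter once per person in an expected 15-20 completers spread over several cohorts. If it shows no difference, a reader will want to know whether the cohorts are alike or the measure is too noisy to separate them. A stability claim resting on this interaction could not answer that.

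**Working it through.** **The plan's own figure.** The only sample-size figure is 8 subjects, to detect a 20% difference between steps of a GLP-1 ramp (CV 30%, power 80%, alpha 0.05). It does not concern control stability. It also does not follow directly from its inputs: taking 30% as the SD of the paired difference, n = (0.30 × (1.960 + 0.842) / 0.20)² = 17.7, so 18 (20 with the t distribution, two-sided). That is a separate matter, and nothing below depends on it.

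**What the control interaction tests.** Controls have no dexamethasone level, so *analysed identically* is taken to mean that visit replaces treatment. For control i at visit v, let D_iv be mean C-peptide at 60-120 min minus mean C-peptide at 0-60 min, and let d_i = D_i2 − D_i1. With two periods and two visits the interaction F-test on 1 and n − 1 degrees of freedom equals the square of the paired t statistic, t = mean(d) / (s_d / √n), where s_d is the SD of the paired change. The within-subject SD is s_w = s_d / √2.

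**Reading 1: no mean drift.** The 95% CI half-width for the mean change is t(0.975, n−1) × s_d / √n.
- n=6: 2.571 / 2.449 = 1.05 s_d, or 1.05 × 1.414 = 1.48 s_w.
- n=10: 2.262 / 3.162 = 0.72 s_d, or 0.715 × 1.414 = 1.01 s_w.

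The true drift detectable with 80% power (noncentral t, two-sided 0.05) is 1.44 s_d at n=6 and 1.00 s_d at n=10. A non-significant result is therefore compatible with sizeable drift, and no margin says how much would be acceptable.

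**Reading 2: repeatability.** With normal changes and no mean shift, t has n − 1 degrees of freedom whatever s_d is, so P(no interaction) = 1 − 0.05 = 0.95 by definition of the test's size. A simulation confirmed this (20,000 runs, 4,000 at n=1000). Its inputs are assumptions: mean effect 20 percentage points, between-subject SD 10, within-subject SD 1 to 40 (intraclass correlation 0.99 to 0.06). The proportion returning no interaction was 0.947 to 0.955 at n = 6, 8, 10, 100 and 1000. On this reading more controls would not help.

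**With a true mean shift.** Adding an assumed 10-point shift gave these chances of no interaction:

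| Within-subject SD (assumed) | n=6 | n=10 |
|---|---|---|
| 5 | 0.216 | 0.023 |
| 10 | 0.707 | 0.485 |
| 20 | 0.890 | 0.828 |

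The noisier the measure, the more often real drift would be missed and the measure called stable.

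**What 6-10 pairs can say about the within-subject SD.** The 95% limits are the estimate times √((n−1)/χ²), with χ² at 0.975 and 0.025.
- n=6: √(5/12.83) = 0.62 to √(5/0.831) = 2.45.
- n=10: √(9/19.02) = 0.69 to √(9/2.70) = 1.83.

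**The case against.** The strongest reply is that the controls were enrolled to detect systematic change over time and repeat testing. For that purpose a comparison of means is the right tool, and *stable* may be shorthand for no shift over a week. This stands in part: the plan is not testing the wrong quantity if drift is all that is meant, and on that reading a tight interval around the mean change would settle the question. But the plan proposes no interval and no margin, so the inference from non-significance still fails.

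A second reply is that the opening words of the ANOVA sentence could describe a separate analysis for each subject, which would expose individual changes. The repeated-measures wording and the comparison of mean values make a group-level analysis the likelier reading.

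A third is that the sentence states an expectation, with no decision attached, and that Aim 3 is not formally conditional on it. That is correct and limits the consequence. The sentence is still the only conclusion the plan announces for this arm.

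A reader might also infer that the fasting GLP-1 effect is mostly noise, or that the dexamethasone result and the Aim 3 comparison are unsound. The documents support neither. They give no visit-to-visit figure, so the size of the noise is unknown. Visit-to-visit variation is already in the error term of the dexamethasone interaction and in the spread within Aim 3 cohorts, so it costs power but does not by itself create false differences.

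**Conclusion.** The inference is unsupported on both readings. For drift, non-significance leaves a 95% interval of about ±1.05 (n=6) to ±0.72 (n=10) SDs of the paired change, judged against no margin. For repeatability, the test gives the same answer about 95% of the time whether subjects repeat closely or hardly at all, provided the mean does not move.

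The half-widths assume roughly normal paired changes and a group-level analysis with visit as the second factor. The 95% figure needs the same assumptions and does not depend on the simulated SDs; the results with a 10-point shift do, and are illustrations only.

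The effect is on what may be concluded from the control arm and from a null Aim 3 result. The validity of the dexamethasone interaction test and of the Aim 3 cohort comparison is not affected.

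**What to change.** Replace the sentence that infers stability from a missing interaction. For each control, compute the fasting GLP-1 effect at both clamps, on the C-peptide scale and in the percentage form Aim 3 uses. The ANOVA on C-peptide means does not directly test the percentage form. Then report:

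- **Drift:** the mean between-visit change with its 95% CI. The interaction test may stay beside it but should not carry the conclusion.
- **Repeatability:** the within-subject SD (SD of the paired change divided by √2) and the 95% limits of agreement, each with a confidence interval.

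Base any statement of stability on these estimates, say which meaning is intended, and set the within-subject SD beside the Aim 3 cohort differences when interpreting them.

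This needs no extra subjects, visits or samples, because the paired control clamps are already planned; it is a few lines of analysis and a reworded sentence. The price is a more cautious claim, since the within-subject SD has 95% limits of 0.62-2.45 times the estimate at n=6 and 0.69-1.83 times at n=10. Repeatability in healthy controls will also carry over only imperfectly to the Aim 3 subjects with diabetes.
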